4.1.3 Number of Study Sites

The Yale School of Medicine campus will be the only study site. Research procedures will take place at two sites: The Yale Magnetic Resonance Research Center (MRRC) and the Yale Center for Clinical Investigation (YCCI) Church Street Research Unit. The YCCI Research

Unit will be used as a backup for some of the longer clinical and psychometric evaluations (e.g., Visit 1).

4.2 Outcome Variables

4.2.1 Primary Outcome Variables

1) Quality of life in Neurological Disorders (Neuro-QoL) Scores

Timeframe: This measure will be collected at baseline (T0), immediately after 6 weeks of intervention (T1), and 12 weeks thereafter (T2) from all subjects.

Rationale: The Neuro-QoL is a set of self-report measures that assesses the health-related quality of life of adults and children with neurological disorders. Neuro-QoL instruments were developed through a collaborative, multisite NINDS-sponsored research initiative to construct psychometrically-sound and clinically-relevant health-related quality of life measurement tools for individuals with neurological conditions including PD. The Neuro-QoL instruments enable within-disease as well as cross-disease comparisons and are intended for use in both neurology clinical trials and clinical practice. We will use the Neuro-QoL version 2 Cognitive Function item bank to assess post-training self-reported changes in cognitive functions.

Change in the Neuro-QoL version 2 Cognitive Function scores from T0 to T1 and across T2 will be the primary cognitive outcomes of this study. Significant increase in the Cognitive Function scores at T1 will be considered significant improvement in self-reported cognitive function in everyday life. Significant increase in these scores across T2 will be considered sustained improvement in self-reported cognitive function in everyday life.

2) Questionnaire on Mental Imagery (QMI) Vividness of Imagery Scale scores

Time frame: This measure will be collected at baseline (T0), immediately after 6 weeks of intervention (T1), and 12 weeks thereafter (T2) from all subjects.

Rationale: The QMI is a measure of vividness of an individual's multisensory and motor imagery on a scale of 1 to 7 (1: perfectly vivid image, 7: no image present at all).

Change in the QMI scores from T0 to T1 and across T2 will serve as the manipulation check for the mental imagery intervention. Significant increase in these scores at T1 will be considered improved imagery vividness. Significant increase in these scores across T2 will be considered sustained improvement in imagery vividness.

3) Task-specific whole-brain pairwise functional connectivity

Time frame: This measure will be collected at baseline (T0), immediately after 6 weeks of intervention (T1), and 12 weeks thereafter (T2) from all subjects.

Rationale: We will calculate the whole-brain pairwise functional connectivity during mental imagery and video-watching of naturalistic goal-directed tasks in the MRI scanner for each subject.

Change in task-specific pairwise functional connectivity from T0 to T1 and across T2 will be the primary imaging outcomes of the study. Significantly increased task-specific pairwise functional connectivity in major networks (e.g., default mode network during mental imagery and frontoparietal executive network during video-watching) at T1 will be considered improved task-specific functional reorganization of these networks. Significantly increased task-specific pairwise functional connectivity in major networks across T2 will be considered sustained

improvement in task-specific functional reorganization of these networks.

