2.3.2 Potential Benefits

Immediate potential benefits

Subjects with PD in the experimental group will most likely experience a direct benefit from the mental imagery intervention in terms of improvement in cognitive functioning in everyday life. Similarly, subjects with PD in the active control group will most likely experience a direct benefit from psychoeducation in terms of gathering information about cognitive problems experienced in PD and management and coping strategies.

Long-Range Potential benefits

The knowledge gained from this study will facilitate the design and implementation of a phase 2 clinical trial. Ultimately, it is highly likely that mental imagery training will be incorporated into cognitive rehabilitation programs and will lead to improvements in the treatment of cognitive problems of individuals with PD.

3 Study Purpose and Objectives

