3.1 Hypotheses

We hypothesize that our 6-week mental imagery training protocol will improve goal-directed cognitive functioning in everyday life of PD patients. Furthermore, we predict the effects of mental imagery will increase task-specific whole-brain functional connectivity and improved differentiation of core brain networks. We hypothesize that the training effects on A)

goal-directed cognitive functioning and B) functional network re-organization will be sustained over the course of 12 weeks post-intervention in the PD-MI group, but not in the PD-Con group.

Lastly, we hypothesize that the putative task-specific within- and between-network functional connectivity changes in the PD-MI group at the 6- and 12- week timepoints will predict the corresponding self-reported, performance-based, and executive function test outcomes.

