5.4 Statistical Method

5.4.1 Statistical Design

This is a phase 1 randomized clinical trial aiming to enroll 120 subjects with Parkinson's disease (PD) assigned in parallel to the experimental PD-MI (N=60) and active control PD-Con (N=60) groups. The units of observation are the subjects in these groups. Subjects will be enrolled continuously and randomized to two groups using the "minimization" method.¹⁰¹ After truly randomly allocating the first 10 subjects, each subsequent subject will be allocated to either group considering the factors age, gender, and disease stage. This method will allow us to minimize the imbalance between the groups in terms of demographic and clinical characteristics while at the same time preserving the randomness of group allocation.

We will use independent-sample t-tests and nonparametric Mann-Whitney U tests to compare subjects characteristics between the PD-MI and PD-Con groups.

We will use mixed ANOVA tests with interaction terms to assess the short- and longer-term changes in cognitive and imaging outcomes before and after training.

Our overall statistical approach is designed to address the outcomes of four different aims:

AIM 1: To determine the effects of mental imagery training on goal-directed everyday cognitive functioning in PD

Primary outcome: Change in Neuro-QoL version 2 Cognitive Function scores.⁹⁷

Manipulation check: Change in QMI Vividness of Imagery Scale scores.¹⁰⁰

Neuro-QoL version 2 Cognitive Function scores (Visit 1) and QMI scores (Visit 2) obtained at baseline and immediately upon conclusion of the 6-week intervention (Visit 3) will be compared between the PD-MI and PD-Con groups using a 2x2 mixed ANOVA with an interaction term (dependent variables: test scores, between-subject factor: group, within-subject factor: time with two levels, i.e., baseline and post-training, interaction: group-by-time) ($p < 0.05$, two-tailed).

Secondary outcomes: Change in composite z-scores obtained from the executive function tests.

We will calculate a composite z-score from the executive function test scores (i.e., Stroop,⁹⁴ F-A-S letter fluency,⁹⁵ and Trail Making A-B tests⁹⁶) for all subjects.

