The primary, secondary and exploratory outcomes as outlined in Aims 1 and 2 will also apply to Aim 3. All cognitive and functional MRI tasks will be repeated 12 weeks after the completion of the training program (Visit 4). These results will then be compared with those obtained at baseline and 6-week post-intervention using a 3x2 mixed ANOVA with an interaction term (dependent variables: cognitive test scores and functional connectivity and graph measures, between-subject factor: group, within-subject factor: time with three levels, i.e., baseline, 6-weeks post-intervention, and 12-weeks post-completion, interaction: group-by-time) ($p < 0.05$, two-tailed). A significant interaction will be followed by post hoc simple effects tests to determine the level(s) of interaction.

AIM 4: To explore the brain-cognition link associated with mental imagery training in PD

Exploratory Aim: We will examine the post-training brain-cognition relationship at the 6-week and 12-week timepoints in each group. We will test whether the post-training changes in task-specific whole-brain pairwise functional connectivity and graph measurements will predict the post-training differences in the Neuro-QoL Cognitive Function and composite executive test scores in each group.

Exploratory outcomes: This brain-behavior relationship at 6 weeks will be the exploratory outcome of Aim 2 and that at 12 weeks will be the exploratory outcome of Aim 3.

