5.4.2 Sample Size Considerations

We calculated the sample size based on the primary cognitive outcome, i.e., Neuro-QoL version 2 Cognitive Function scores. The Neuro-QoL Cognitive Function validation study with 120 PD patients who had mild disease (Hoehn & Yahr stage 2) showed mean \pm SD = 50.46 \pm

7.25.⁹⁷ A change of 2-6 T-scores have been considered a minimally important change in patient-reported outcome measures.¹⁰³

We estimated the sample size based on the assumption that there will be an average of 4 T-score improvement after mental imagery training using the G*Power 3.1 software^{104,105}. The repeated-measures ANOVA between-subject factor model with two groups and two measurements, with an effect size of $f=0.266$ (corresponding to a moderate effect size $d=0.53$), alpha 0.05, and power 0.80 yielded a total sample size of 86 (43 in each group). With an estimated 15% drop out ($86/0.85 \approx 101$) during the 6-week intervention period and another 15% drop out ($101/0.85 \approx 120$) in the subsequent 12-week period, we plan to recruit 120 subjects in total.

In our previous work with PD patients using motor (N=22) and visual (N=22) imagery training, we showed robust task-specific pairwise functional connectivity changes post-training especially in the respective motor and visual networks.⁴ Therefore, we think this sample size will also be adequate for the primary imaging outcome.

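### The rule for reading a rise at T1 (or across T2) as improvement does not refer to the control arm, and for Aim 1 the plan does not say that the group-by-time interaction decides

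*Combined protocol and SAP*

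**What the plan says.** Section 4.2.1, repeated in the synopsis, defines what counts as improvement on the Neuro-QoL Cognitive Function score: "Significant increase in the Cognitive Function scores at T1 will be considered significant improvement in self-reported cognitive function in everyday life". The same form, a significant rise at T1 or across T2, is used for imagery vividness and pairwise connectivity in 4.2.1. In 4.2.2 it is used for the executive composite, the graph measures, the Modified Six-Elements Test and the RBANS. Only the brain-cognition outcome has no such rule. None of these sentences mentions PD-Con, and none refers to section 5.4.1.

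Section 5.4.1, Aim 1, says that baseline and Visit 3 scores "will be compared between the PD-MI and PD-Con groups using a 2x2 mixed ANOVA with an interaction term". It lists the group factor, the time factor and their interaction, with a two-sided 5% level. It does not say which term decides. For Aim 3 it goes further: "A significant interaction will be followed by post hoc simple effects tests to determine the level(s) of interaction".

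In section 3.1, the T1 hypotheses name no comparator. The hypothesis for the later time point says that effects will be "sustained over the course of 12 weeks post-intervention in the PD-MI group, but not in the PD-Con group". Section 5.4.2 bases the sample size on the assumption that "there will be an average of 4 T-score improvement after mental imagery training". It states no change for the control arm and uses the between-subject factor model.

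**The concern.** The sections point to different terms of one model. A rise at T1, as in 4.2.1, fits the time main effect or a pre-post test within PD-MI. Aim 1 in 5.4.1 points to the interaction without making it decisive. The between-subject factor model in 5.4.2 tests the group main effect, averaged over both visits. Only the interaction isolates the randomised comparison of change.

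The choice matters because the primary cognitive outcome is self-reported and the arms look different to participants: one-on-one imagery sessions against pre-recorded lectures. Retest effects and expectancy could raise scores in both arms, and a pre-post reading would credit that rise to imagery training.

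The documents show how such a reading arises. Section 1.2 reports that in the team's previous randomised trial the neurofeedback signal did not rise significantly more in the motor imagery arm than in the visual imagery arm, while timed motor performance improved in both. The synopsis then cites that work as having improved motor performance. Both arms of that trial practised imagery, so the statement is not false, but it is a pre-post statement. The present trial has a non-imagery control precisely so that it need not rely on one.

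**Working it through.** **Inputs from the documents.** SD 7.25; 120 recruited; 15% dropout during the 6-week intervention (5.4.2); two-sided alpha 0.05 (5.4.1). Expected completers at Visit 3: 120 x 0.85 = 102, or 51 per arm.

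**Assumptions.** The correlation rho between visits is not stated; 0.5 is used, with 0.3 and 0.7 as a range. Both arms rise equally by 2 to 3 T-score points, so there is no true difference. This shared rise is not in the documents; it lies at the low end of the 2 to 6 points that 5.4.2 cites as a minimally important change.

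**Step 1: the plan's own figure.** For the between-subject factor model with m = 2 measurements, lambda = f² x N x m / (1 + (m - 1) x rho). With f = 0.266, N = 86 and rho = 0.5: 0.0708 x 86 x 2 / 1.5 = 8.11. On 1 and 84 df this gives power 0.804, so the stated 86 reproduces at rho = 0.5. Dropout: 86/0.85 = 101.2 and 101/0.85 = 118.8, consistent with 120. The term being powered is the group main effect.

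**Step 2: SD of change.** 7.25 x sqrt(2 x (1 - rho)) = 7.25 at rho = 0.5.

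**Step 3: three readings of a significant result, rho = 0.5, 51 per arm.**
- Rise within PD-MI: SE = 7.25/sqrt(51) = 1.015. Noncentrality is 2/1.015 = 1.97 and 3/1.015 = 2.96; the critical t on 50 df is 2.009. The probability of a significant rise is 0.49 and 0.83.
- Time main effect: SE = 7.25/sqrt(102) = 0.718. Noncentrality is 2.79 and 4.18; the critical t on 100 df is 1.984. The probability is 0.79 and 0.985.
- Group-by-time interaction: the shared rise cancels in the difference of changes, so noncentrality is 0. It is significant in 5% of trials, 2.5% in favour of PD-MI, whatever the size of the shared rise.

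**Step 4: sensitivity (shared rise of 2 to 3 points).**

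| rho | per arm | PD-MI rise significant | time effect significant | interaction favours PD-MI |
|---|---|---|---|---|
| 0.3 | 51 | 37% to 69% | 65% to 94% | 2.5% |
| 0.5 | 51 | 49% to 83% | 79% to 98.5% | 2.5% |
| 0.7 | 51 | 70% to 96% | 95% to over 99% | 2.5% |
| 0.5 | 43 | 42% to 76% | 72% to 97% | 2.5% |

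A simulation of 20,000 trials per setting at 43 per arm, with shared rises of 0, 2 and 4 points and rho 0.5 and 0.7, put the two-sided interaction rate at 4.7% to 5.2%.

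**The case against.** The best defence is that 4.2.1 only describes how a rise in a score is read and does not use the word success. The test is in 5.4.1, it compares the arms, and the 5% level is printed directly after the interaction. No within-arm test is planned for Aim 1. This stands in part: the interaction is planned, and it is the natural reading of 5.4.1. It does not settle the matter, because the only sentences that say what result will be called improvement are those in the synopsis, 4.2.1 and 4.2.2, and 5.4.1 does not override them for Aim 1.

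A reader might infer more than the documents support:
- *That a shared rise will count as trial success.* It can be read so from 4.2.1 alone, but 5.4.1 specifies a comparison that a shared rise does not satisfy beyond the nominal error rate.
- *That the 3.1 hypothesis will be judged by one arm being significant and the other not.* Ungated, with no true difference, that pattern has probability p(1 - p): 0.49 x 0.51 = 25% and 0.83 x 0.17 = 14% at rho = 0.5. But this hypothesis concerns the 12-week effect, where Aim 3 allows simple effects tests only after a significant interaction. A two-visit approximation of that gate brings the rate to about 2%.
- *That the protocol predicts a Neuro-QoL rise in controls.* Section 2.3.2 does say that "subjects with PD in the active control group will most likely experience a direct benefit from psychoeducation", but the sentence goes on to describe information and coping strategies, not a score change.
- *That regression to the mean would lift both arms.* Entry is not selected on low Neuro-QoL scores, so this is not a supported mechanism.

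**Conclusion.** The point holds as a mismatch between the stated rule and the planned test. The synopsis, 4.2.1 and 4.2.2 define improvement without the control arm. Section 5.4.1 plans the right comparison but does not make it decisive for Aim 1, and 5.4.2 is sized on yet another term. With a shared rise of 2 to 3 points and no true difference, the literal rule would be met in 49% to 83% of trials (PD-MI rise) or 79% to 98.5% (time effect), against about 2.5% for an interaction falsely favouring PD-MI.

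The large percentages belong to the literal reading of 4.2.1; they are not the error rate of the planned analysis. They rest on the assumed shared rise and correlation, with SD 7.25 and 51 per arm taken from the plan. The amendment should be made because the rule is fixed in advance and, as written, permits a pre-post claim.

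**What to change.** - **Synopsis, 4.2.1 and 4.2.2** (except the brain-cognition prediction outcome): define success as a significant group-by-time interaction with the PD-MI minus PD-Con difference in change from T0 in the direction of benefit. State that direction for each outcome. For imagery vividness this needs care, since the scale is described as running from 1 (vivid) to 7 (no image) while a rise is called improvement.
- **5.4.1:** say for Aim 1, and for the parallel analyses in Aim 2, that the interaction decides, and that the time main effect and within-arm tests are descriptive. Keep the existing Aim 3 gate.
- **3.1:** word the hypotheses as between-arm differences at T1 and T2.

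This changes wording only; the planned model, data collection and sample size are untouched. The one small cost is that gains shared by both arms no longer count as improvement.

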2) Questionnaire on Mental Imagery (QMI) Vividness of Imagery Scale scores

Time frame: This measure will be collected at baseline (T0), immediately after 6 weeks of intervention (T1), and 12 weeks thereafter (T2) from all subjects.

Rationale: The QMI is a measure of vividness of an individual's multisensory and motor imagery on a scale of 1 to 7 (1: perfectly vivid image, 7: no image present at all).

Change in the QMI scores from T0 to T1 and across T2 will serve as the manipulation check for the mental imagery intervention. Significant increase in these scores at T1 will be considered improved imagery vividness. Significant increase in these scores across T2

will be considered sustained improvement in imagery vividness.

3) Task-specific whole-brain pairwise functional connectivity

Time frame: This measure will be collected at baseline (T0), immediately after 6 weeks of intervention (T1), and 12 weeks thereafter (T2) from all subjects.

Rationale: We will calculate the whole-brain pairwise functional connectivity during mental imagery and video-watching of naturalistic goal-directed tasks in the MRI scanner for each subject.

Change in task-specific pairwise functional connectivity from T0 to T1 and across T2 will be the primary imaging outcomes of the study. Significantly increased task-specific pairwise functional connectivity in major networks (e.g., default mode network during mental imagery and frontoparietal executive network during video-watching) at T1 will be considered improved task-specific functional reorganization of these networks.

Significantly increased task-specific pairwise functional connectivity in major networks across T2 will be considered sustained improvement in task-specific functional reorganization of these networks.

Secondary and Exploratory Outcome Variables

1) Composite executive function test scores (Secondary)

Time frame: This measure will be collected at baseline (T0), immediately after 6 weeks of intervention (T1), and 12 weeks thereafter (T2) from all subjects.

Rationale: We will calculate the composite z-scores of the executive function test scores (i.e., Stroop, F-A-S letter fluency, and Trail Making A-B tests) for all subjects.

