Online Homework and Quizzes: These will administered via the Yale REDCap online survey platform. Responses will be exported from REDCap.

- Quizzes on the psychoeducation material for the PD-Con group
- Surveys on the content of mental imagery homework for the PD-MI group

Clinical and Cognitive Evaluations:

- MDS-UPDRS and Hoehn & Yahr to assess disease severity (Visit 1)
- Wechsler Test of Adult Reading to determine premorbid IQ (Visit 1)
- RBANS test and executive function tests (Stroop, letter fluency (F-A-S), and Trail Making Test parts A and B) for a comprehensive cognitive evaluation (Visits 1, 3, and 4)
- Neuro-QoL survey (primary cognitive outcome) to assess the impact of cognitive functioning on activities of daily living (Visits 1, 3, and 4)
- Structured cognitive interview for the PD-MI group to determine subjects' cognitive difficulties during everyday tasks (Visit 1)
- QMI Vividness of Imagery Scale will serve as a manipulation check for the mental imagery intervention (Visits 2, 3, and 4)

- Modified Six-Elements Test as a performance-based measure of goal-directed planning and execution (Visits 1, 3, and 4)

Case report forms for each subject will be used to enter clinical evaluation results, and scores of paper-pencil tests, online surveys, and performance-based tests. All of this information will then be entered into a password-protected electronic database, which will be stored in a group-owned ([name] Lab) shared space on a Yale REDCap database.

Imaging Data:

Functional MRI data during mental imagery and video-watching tasks will be collected in a 3 Tesla human magnet at the MRRC (Visits 2, 3, and 4). The fMRI data will be used for functional connectivity analyses to evaluate the changes in whole-brain functional connectivity (primary imaging outcome) and other network measures as a result of the mental imagery intervention.

Imaging data will be transferred securely to workstations for analysis and stored on HIPAA-compliant secure central storage servers ("Storage@Yale") provided by the Yale IT Department for a monthly fee.

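### The QMI interpretation rule runs against its own scale: lower scores mean more vivid imagery, yet a significant increase is to be read as improvement

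*Combined protocol and SAP*

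**What the plan says.** Section 4.2.1, item 2, lists the QMI under the primary outcome variables and gives its scale: "on a scale of 1 to 7 (1: perfectly vivid image, 7: no image present at all"). Two reading rules follow. For T1: "Significant increase in these scores at T1 will be considered improved imagery vividness". For T2: "Significant increase in these scores across T2 will be considered sustained improvement in imagery vividness". The Synopsis, under Primary Outcome Variables item 2, has the same anchors and the same two rules; its T2 sentence likewise says that an increase "will be considered sustained improvement in imagery vividness".

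The role of the measure is clear. Section 5.1.1 says: "QMI Vividness of Imagery Scale will serve as a manipulation check for the mental imagery intervention". Section 5.4.1, Aim 1, names Neuro-QoL Cognitive Function as the primary outcome and gives the QMI its own line: "Manipulation check: Change in QMI Vividness of Imagery Scale scores". On the analysis, it says that "QMI scores (Visit 2) obtained at baseline and immediately upon conclusion of the 6-week intervention (Visit 3) will be compared between" the two groups in a 2x2 mixed ANOVA with a group-by-time interaction, two-tailed at 0.05. That section gives no direction for the QMI.

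**The concern.** On a scale where 1 is the most vivid image and 7 is no image, a rise in score is a fall in vividness. The rule calls that rise an improvement. It is also the only place where the plan says which direction of QMI change counts as success, because the two-tailed test in section 5.4.1 leaves direction open.

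The manipulation check shows whether six weeks of training changed imagery at all, and so it helps in interpreting the Neuro-QoL result, whether positive or null. Under the rule as written, training that made imagery more vivid would not be credited, and training that made it less vivid would be reported as having worked. If the direction is corrected only after the data have been seen, the correction becomes a post hoc change to a prespecified rule.

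**Working it through.** **Step 1: anchors against rule.**

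| Source | Scale | Rule at T1 | Rule at T2 |
|---|---|---|---|
| Synopsis, item 2 | 1 most vivid, 7 no image | increase = improved | increase = sustained improvement |
| Section 4.2.1, item 2 | 1 most vivid, 7 no image | increase = improved | increase = sustained improvement |

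An increase moves a score towards 7, that is, towards no image. All four rule sentences therefore point the wrong way for a score on the stated scale.

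**Step 2: is the score reversed anywhere?** The rule would be right if ratings were recoded so that higher meant more vivid.

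- Section 5.1 (Visits 2 and 3), section 5.1.1 and section 5.3.3 say when the QMI is given and what it is for, but not how it is scored.
- Section 5.4.1 gives the test but no direction.
- Section 5.4.3 defines scores for the executive composite, the RBANS and the Modified Six-Element Test, but not for the QMI.
- The QMI form and the case report form are listed as attachments and were not available, so scoring there cannot be checked.

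No reversal is stated in the text that can be read.

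**Step 3: how often the label would go wrong (illustration).** The plan gives no QMI standard deviation, expected change or power figure, so there is nothing of its own to reproduce here. The effect sizes below are assumptions.

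*Inputs.* 120 are randomised, 60 per group (sections 4.3.1 and 5.4.1). Section 5.4.2 allows 15% loss "during the 6-week intervention period and another 15% drop out" in the following 12 weeks. At T1: 120 × 0.85 = 102, or 51 per group. The test is two-sided at 0.05 (section 5.4.1).

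*Reading.* A significant increase or decrease is taken as the T1 group-by-time interaction. Section 4.2.1 itself names no group comparison.

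*Formula.* In a 2x2 mixed ANOVA the interaction is equivalent to a two-sample t-test on change from baseline. Let d be the fall in QMI in PD-MI minus the fall in PD-Con, divided by the SD of change. With n per group, df = 2n − 2 and the noncentrality is −d√(n/2). The probability of a significant decrease is P(T < −t_crit), with T noncentral t.

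For n = 51: df = 100, t_crit = 1.984, √(51/2) = 5.05.

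| True gain in vividness, d | Noncentrality | P(significant decrease), 51 per group | Same, 60 per group (no dropout) |
|---|---|---|---|
| 0.2 | −1.01 | 16.9% | 19.1% |
| 0.5 | −2.52 | 70.6% | 77.5% |
| 0.8 | −4.04 | 97.9% | 99.1% |

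Each entry is the chance of a significant gain that the rule does not credit. By symmetry, a true loss of the same size would be labelled an improvement with the same probability. With no true difference, the improved label appears 2.5% of the time whichever direction is specified, so the null case shows no added error. A simulation of 400,000 trials at 51 per group gave 2.5%, 16.9%, 70.5% and 97.9% for d = 0, 0.2, 0.5 and 0.8. No figure was computed for T2.

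**The case against.** The strongest reply is that little depends on this sentence. The test is two-tailed, so its p-value is the same either way. No stopping rule, other analysis or claim is made conditional on the QMI. The anchors stand just before the rule, so an analyst would have to overlook them to mislabel the result. Other imagery evidence is also planned: a content score from the descriptions recorded in the scanner, compared between groups at T1, and diary vividness ratings in the PD-MI group. All of this stands, and it limits the harm to the label on the manipulation check. It does not make the rule correct, and neither of the other measures replaces a vividness scale completed by both groups.

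Second, the anchors describe how items are rated. The text does not say how ratings become a score, and an attached form might reverse them. That is possible. Even then, the printed anchors and the printed rule would still disagree, and the reversal would need to be stated.

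Third, the probabilities above are ordinary t-test power at assumed effects. They do not measure how likely an analyst is to follow the rule literally. That is a fair limit; the contradiction does not depend on them. An interaction can also reach significance through change in PD-Con alone, so reading it as a decrease in PD-MI is a simplification.

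Fourth, Aim 3 in section 5.4.1 does not name the QMI. It carries the Aim 1 and 2 outcomes forward to the three-timepoint ANOVA. Because section 4.2.1 lists the QMI as a primary outcome variable, it can reasonably be taken as included, but that is an inference.

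**Conclusion.** The concern holds. On the plan's own anchors the direction is inverted in four sentences, two in the Synopsis and two in section 4.2.1, and no readable text states a reversal that would put it right. It should be fixed, since it misstates how the designated manipulation check is to be read, but it does not threaten the primary analysis: the planned tests, the sample size, and the Neuro-QoL and connectivity conclusions do not change. The conclusion about direction needs no numerical assumption. It would change only if the unseen forms reverse the score, and the protocol would then need to say so. The illustrative 16.9% to 97.9% at T1 rests on assumed effects of 0.2 to 0.8 SD of change, 51 per group, and the interaction reading of the rule.

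**What to change.** Change 'increase' to 'decrease' in the four QMI sentences: the T1 and T2 rules in the Synopsis (Primary Outcome Variables, item 2) and in section 4.2.1, item 2. Leave the planned tests in section 5.4.1 as they are.

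Alternatively, keep 'increase' and add one sentence to section 5.4.3 saying that each QMI rating is reversed before analysis, as 8 minus the rating, so that higher means more vivid. If an attached form already does this, section 5.4.3 should say so.

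The cost is one word in each of four sentences, or one scoring sentence. No test, contrast, sample size or study procedure changes. The amendment should be made before QMI results are analysed, so that the direction remains prespecified.
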